11.4.5.2 Urine pregnancy test

Female subjects of childbearing potential will have a urine pregnancy test (human chorionic gonadotropin; dipstick) performed at the trial site at baseline prior to treatment assignment. The test will be repeated at Week 4 and thereafter the schedule of pregnancy testing is as shown in the schedule of trial procedures (Section 4). After May 2021, subjects must in addition to the test performed at the trial site, perform the urine pregnancy test at home within 48 hours before the telephone visit using the kit supplied by the site staff. The subject will also be provided with a urine pregnancy test instruction. The result of the pregnancy test should be communicated to the site during the telephone visit and documented in the eCRF and source documents.

For female subjects who become of childbearing potential during the trial (defined as Tanner stage ≥3 [Marshall 1969] or menarche), the investigator must reassess whether contraceptive measures are in place (if applicable), and perform the pregnancy tests according to the schedule of trial procedures (Section 4).

Note that pregnant subjects must permanently discontinue IMP and be withdrawn from the trial immediately (see Section 10.2.2).

11.4.5.3 Investigator evaluation of laboratory samples

Central laboratory

Chemistry, haematology, urinalysis (if applicable), serology, and serum pregnancy tests will be analysed by a central laboratory, which will provide results to the trial sites. The investigator must evaluate all results outside the reference range ('clinically significant' or 'not clinically significant') and sign and date the evaluation. The signed and dated version will be filed with the investigator's trial documentation. Clinically significant abnormal tests at baseline or later must be repeated to confirm the abnormality.

At each visit, the site staff will record in the eCRF if a sample was taken and, if applicable, the date and time as well as the investigator's assessment of the results ('normal', 'abnormal, not clinically significant', 'abnormal, clinically significant').

If a screening laboratory result is abnormal and of clinical significance, it will be at the investigator's discretion to decide if the subject should be included in the trial (in accordance with exclusion criterion no. 28).

Trial ID: LP0162-1337 Date: 21-Feb-2022

Version: 14.0 Page 90 of 187

A laboratory manual will be provided to the trial sites specifying the procedures for collection, processing, storage, and shipment of samples, as well as laboratory contact information specific to this trial.

Tests performed at the trial site

Urine samples will be tested at the trial site with a dipstick. Until end of May 2021, in case of abnormal dipstick results, a urine sample was sent to the central laboratory for microscopic examination (leucocytes, erythrocytes, and casts). After May 2021, a urine sample will only be sent to the central laboratory to perform urinalysis if considered required by the investigator based on the urine dipstick results.

At each site visit, the site staff will record in the eCRF if a urine sample was taken and, if sent for central laboratory analysis following an abnormal dipstick result, the investigator's assessment of the central analysis result ('normal', 'abnormal').

Reporting in eCRF

Clinically significant abnormal laboratory results at the screening visit will be documented as medical history in the eCRF. At subsequent visits, any clinically significant deterioration of a pre-existing condition as well as any new clinically significant sign, symptom or illness will be reported as an AE in accordance with Section 13.3.

11.4.6 Anti-drug antibodies measurements

Blood samples will be collected to determine tralokinumab ADA levels at pre-determined time points according to the schedule of trial procedures (Section 4). It will be recorded in the eCRF if the sample was taken; if the sample was not taken, a reason will be provided.

Collection, handling, and shipment instructions for ADA blood samples are provided in a laboratory manual.

Serum samples for determination of presence or absence of ADA will be analysed by a laboratory using a validated bioanalytical method. A tiered testing scheme will be used, with the first step being screening. Samples found positive in the screening step will be tested in the confirmatory step. Samples confirmed positive for ADA in the confirmatory step will undergo endpoint titre determination and will be analysed for the presence of neutralising antibodies (nAB). Details of the analytical method used will be described in an ADA bioanalytical report.

11.5 Pharmacokinetic assessments

Blood samples for PK assessments should be collected at the time points specified in the schedule of trial procedures (Section 4). It will be recorded in the eCRF if the PK sample was taken; if the sample was not taken, a reason will be provided.

Collection, handling, and shipment instructions for PK blood samples are provided in a laboratory manual.

Serum samples for determination of tralokinumab concentrations will be analysed by a laboratory using validated bioanalytical methods. Details of the analytical methods used will be described in the bioanalytical report.

11.6 Skin biopsies (subgroup of subjects at selected sites)

At selected sites, the subgroup of subjects who donated skin biopsy samples in the parent trial LP0162-1325 will be asked to have skin biopsies taken in trial LP0162-1337 as well. The objective of collecting these additional biopsies is to investigate the molecular profile in the skin of AD patients treated for more than 1 year with tralokinumab and to document the long-term disease control of tralokinumab. Participation in this part of the trial requires that the subject provides additional informed consent.

Two 3 mm skin biopsies (1 from lesional skin and 1 from non-lesional skin) will be taken at Week 48 as specified in the schedule of trial procedures (Section 4). The locations of the biopsies taken should be in close proximity to the locations of the biopsies taken in trial LP0162-1325.

Collection, handling and shipment instructions for skin biopsy samples are provided in a separate laboratory manual.

The biopsies will be analysed for expression of markers of inflammation and skin barrier integrity by gene expression analysis.

The biomarkers to be analysed include, but are not limited to, the following:

Gene expression analysis

- Global gene expression analysis by RNA sequencing.
- Quantitative realtime polymerase chain reaction (qPCR) analysis of the following genes: IL-1B, IFNG, IL-13, IL-31, CCL17 (TARC), CCL26, C-X-C motif chemokine ligand 10 (CXCL10), CCL20, IL-17A, IL-20, IL-22, S100A9, S100A12.

The results from the analyses of biopsy material will be presented in a separate report.

11.7 Estimate of total blood volume collected

Blood samples will be drawn for analysis of safety (chemistry, haematology, and serology), PK, and ADA.

The total volume of blood to be drawn for each subject will depend on the time of their entry in the trial and the local duration of the trial (Appendix 3J). For adult subjects, the total blood volume drawn will be approximately 265 mL until end of May 2021, plus 70 mL per year of trial participation after May 2021. For adolescents, the total amount of blood drawn until end of May 2021 will be approximately 130 mL, plus 70 mL for the 1 year extension until end of May 2022.

The volume of blood drawn at any visit during the trial will be approximately 20 mL for all subjects. The maximum possible blood volume drawn at one visit is less than 1% of the total blood volume, and the maximum possible blood volume drawn within 4 weeks is less than 3% of the total blood volume, as recommended for the age group 0–18 years (European Commission 2008).

11.8 End of trial

An **end of treatment form** must be completed in the eCRF for all subjects completing treatment. The following data will be collected:

• Date of last administration of IMP.

An **end of trial form** must be completed in the eCRF for all subjects assigned to treatment. The following data will be collected:

- Did the subject complete the trial?
 - *If not*: primary reason for withdrawal from trial (lack of efficacy, AE, withdrawal by subject, withdrawal by parent/guardian*, lost to follow-up, death, other).
- Did the subject attend the safety follow-up visit?
 - *If not*: primary reason for not attending safety follow-up visit (lack of efficacy, AE, withdrawal by subject, withdrawal by parent/guardian*, lost to follow-up, death, other).
- Date of last contact.

^{*}For adolescent subjects as applicable.

Page 93 of 187

The end of trial form will be completed when the subject has had their last visit (see Section 7.3).

11.9 Storage of biological samples

PK blood samples will be retained for as long as the quality of the material permits evaluation but for no longer than 12 months after completion of the clinical trial report (CTR).

Samples for ADA evaluation will be retained for as long as the quality of the material permits evaluation but for no longer than 15 years after marketing authorisation.

Skin biopsy samples will be retained for as long as the quality of the material permits evaluation but for no longer than 12 months after completion of the CTR unless specific additional consent has been obtained that allows storage for future research (see below).

Biobank

If consent is given by the subject, LEO Pharma will store skin biopsy samples in the biobank established by LEO Pharma and hosted by BioStorage Technologies, Inc. Donation of the samples for future research is voluntary and subjects must give their separate written consent to confirm donation and storage and the terms associated herewith. The samples will be transferred from the relevant laboratory to the biobank. The samples will be labelled with the trial ID, subject ID, and the sample date to protect the privacy of the subjects and to allow continued blinding for future analyses.

12 Scientific rationale for trial design and appropriateness of assessments

This trial is open-label to ensure the generation of long-term safety data without treating subjects with placebo for a prolonged period of time. The trial includes adolescent and adult subjects who have already participated in a clinical trial (parent trial) with tralokinumab. The eligibility criteria are chosen to ensure that subjects from the parent trials can safely be included in this long-term trial. Subjects will have the possibility to use tralokinumab both with and without TCS (US class \geq 4 or Europe class \leq 3), reflecting the intended use of tralokinumab in real clinical practice.

Long-term safety will be assessed using standard clinical methods of subject evaluations, such as AE monitoring, ECG, vital signs, and clinical laboratory measurements. Furthermore, data on antibodies against tralokinumab (ADAs) will be collected and the potential for immunogenicity will be evaluated until the end of the safety follow-up period. The serum samples for determination of presence or absence of ADA, along with blood concentrations of tralokinumab, will be analysed using validated bioanalytical methods.

The clinical efficacy of tralokinumab treatment will be assessed using IGA, EASI, and SCORAD. IGA is a key instrument used in clinical trials to rate the severity of the subject's global AD. EASI is a validated measure used in clinical practice and clinical trials to assess the severity and extent of AD (Hanifin et al. 2001). SCORAD is a validated tool to assess the extent and severity of AD lesions and subjective symptoms (European Task Force on Atopic Dermatitis 1993). The efficacy endpoints IGA score of 0 or 1 and EASI75 are recognised as important endpoints in clinical trials in AD by regulators in the US, EU, and Japan.

The clinical efficacy of tralokinumab treatment will also be assessed using PROs related to disease symptoms, quality of life, general health status, itch, and sleep quality. POEM is a validated questionnaire used to assess disease symptoms in atopic eczema patients in both clinical practice and clinical trials (Charman et al. 2004), and is recommended by the Harmonising Outcome Measures for Eczema for measuring patient-reported symptoms in eczema trials. DLQI/CDLQI is a validated and widely used questionnaire designed to measure the quality of life of dermatological patients (Finlay and Khan 1994, CDLQI Information and Instructions 2018). The EQ-5D-5L is a standardised measure of health status developed by the EuroQol group to provide a simple, general measure of health for clinical and economic appraisal (Greiner et al. 2003).

In order to be able to analyse the endpoints (change from parent trial baseline), subjects from the parent trial LP0162-1334 will continue to assess the CDLQI independent of the age of the subject during participation in ECZTEND. Subjects from the parent trial LP0162-1334 will

perform an adolescent's pruritis NRS with a recall period of the past 7 days, and an eczemarelated sleep NRS with a recall period over the past 7 nights with phrasings tailored to adolescent subjects, independent of the subject's age during participation in ECZTEND. The EQ-5D-5L has not been validated for adolescents and was not assessed in trial LP0162-1334, and is therefore not to be performed in ECZTEND for subjects from the parent trial LP0162-1334.

The trial design has been modified with protocol version 10 to secure long-term safety data of up to 5 years globally. The treatment extension for subjects from the parent trials LP0162-1325, -1326, -1339, -1341, -1342, -1343, -1346, and TRA-WEI-0015-I will be country-specific to allow for treatment with tralokinumab until tralokinumab is available to patients outside the clinical trial setting (Appendix 3J). Subjects from the ongoing adolescent parent trial LP0162-1334 are offered a total treatment extension of 1 year until end of May 2022.

The trial design was modified while the trial was ongoing (effective after May 2021) to decrease the burden of frequent site visits for subjects by introducing a visit schedule more similar to standard practice for home use. To ensure close safety monitoring throughout the treatment period, a mandatory telephone visit will be performed in between site visits.

13 Adverse events

13.1 Definition and classification of adverse events

Adverse events (AEs) and serious adverse events (SAEs) are defined in Appendix 1.

Classification of AEs in terms of severity, causality, and outcome is defined in Appendix 2.

13.2 Collection of adverse event reports

AEs must be collected from the time of first trial-related activity after the subject or subject's legal representative(s) has signed the informed consent form (ICF) until completion of the clinical trial, as defined in Section 7.3. To avoid duplicate reporting, however, any AE with onset before the final visit (safety follow-up visit) in the parent trial should be reported as an AE in the parent trial; for subjects without a safety follow-up visit in the parent trial, any AE with onset before the baseline visit in ECZTEND should be reported as an AE in the parent trial. If ongoing, the AE should also be recorded as medical history in the current extension trial (see Section 11.2.2). AEs with onset after the final visit in the parent trial and after informed consent has been obtained for the present trial, should be recorded as an AE in ECZTEND.

AEs must be assessed by medically qualified personnel.

At all visits, the subject will be asked a non-leading question by the investigator about AEs, for example: "How have you felt since I saw you last?" No specific symptoms should be asked for. At the site visits, it is important that the investigator also observes the subject for any changes not reported by the subject and records these changes.

Clinically significant abnormal findings related to vital signs, physical examination, ECGs, or laboratory tests after the screening visit must be reported as an AE, as described in Sections 11.4.2 to 11.4.5.

13.3 Reporting of adverse events

AEs reported by the subject or observed by the investigator must be recorded on the AE form of the eCRF and should be described in the following manner:

The *AE term* must be in precise English medical terminology (that is, not necessarily the exact words used by the subject). Whenever possible, a specific diagnosis should be stated (for example 'allergic contact dermatitis').

Page 97 of 187

The *duration* of the AE must be reported by the start date and stop date of the event (it will also be recorded if the event is ongoing). In addition, it will be recorded if the AE started prior to start of IMP.

AEs must be classified in terms of severity, causality, and outcome according to the definitions in Appendix 2.

Action taken with IMP: any action taken with IMP as a consequence of the AE must be recorded (dose not changed, dose reduced, dose increased, drug interrupted, drug withdrawn, not applicable, unknown).

Other action taken: any other action taken as a result of the AE must be recorded (none, concomitant medication, concurrent procedure).

13.4 Reporting of serious adverse events

The criteria that define an AE as serious (that is, an SAE) are defined in Appendix 1. SAE criteria are also listed on the SAE Form. On the SAE form in the present extension trial, information regarding the subject's ID and parent trial ID must also be provided.

13.4.1 Investigator reporting responsibilities

Any SAE must be reported to LEO Pharma on the (paper) SAE Form within 24 hours of first knowledge. This report should contain an assessment of available information on seriousness, severity, causal relationship to the IMP or trial procedure, the action taken, the outcome to date, and a narrative description of the course of the event.

The completed SAE form must be faxed or scanned and e-mailed to Global Safety at LEO Pharma using the e-mail address or fax number below:

Global Safety at LEO Pharma

E-mail address: [contact]

[contact]

If relevant, the investigator will enclose other information with the SAE form, such as anonymised reports of diagnostic procedures, hospital records, autopsy reports, etc.

Page 98 of 187

Additionally, Global Safety at LEO Pharma may request further information in order to fully assess the SAE. The investigator must forward such information to LEO Pharma upon request by fax or e-mail (see contact details above).

The investigator must notify the local IRB(s)/IEC(s) of SAEs, as required by current applicable legislation for the concerned country.

SAEs occurring after the completion of the clinical trial, as defined in Section 7.3, should not be routinely sought or collected. However, such events should be reported to Global Safety at LEO Pharma (see contact details above) if the investigator becomes aware of them.

13.4.2 LEO Pharma reporting responsibilities

Global Safety at LEO Pharma is responsible for assessing whether or not an SAE is expected. The relevant reference safety information document for this clinical trial is:

For the IMP, the Investigator's Brochure, edition 19 and subsequent updates must be used.

Global Safety at LEO Pharma will notify the regulatory authorities and concerned investigators of SAEs according to the current applicable legislation for the concerned countries.

The IRB(s)/IEC(s) will be notified of SAEs according to the current applicable legislation for the concerned countries.

For all non-US countries, the following reporting requirements apply: all SAEs which are assessed as causally related to the IMP(s) by either the investigator or LEO Pharma (ICH E2A Guideline), and which are unexpected (Suspected, Unexpected Serious Adverse Reactions [SUSARs]), are subject to expedited reporting to regulatory authorities and IEC(s)/IRB(s) according to the current applicable legislation in the concerned countries. Investigators will be notified of the evolving safety profile of the IMP on an ongoing basis.

For the US, the following reporting requirements apply: all SAEs which are assessed as causally related to the IMP(s) **by LEO Pharma** (Guidance for Industry and Investigators - Safety Reporting Requirements for INDs and BA/BE Studies; Guidance for Clinical Investigators, Sponsors, and IRBs: Adverse Event Reporting to IRBs – Improving Human Subject Protection) and which are unexpected (Serious and Unexpected Suspected Adverse Reactions [IND safety report]) are subject to expedited reporting to regulatory authorities and IRB(s). Investigators will be notified of the evolving safety profile of the IMP on an ongoing basis.

Page 99 of 187

13.5 Expedited reporting of pregnancy

Any pregnancy occurring during the clinical trial must be reported to LEO Pharma within 24 hours of first knowledge using the (paper) Pregnancy Form (Part I). All pregnancies must be followed up until delivery or termination and final outcome must be reported on the (paper) Pregnancy Form (Part II) within 24 hours of first knowledge.

The completed Pregnancy Forms must be faxed or scanned and e-mailed to Global Safety at LEO Pharma. Contact details are given in Section 13.4.1.

Pregnant subjects must immediately discontinue IMP permanently (Sections 10.2.2 and 10.3).

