Weeks since first treatment in LP0162- 1337	-2	0	2	4	8	16	24	32 64 96 128 160 192 224 256	40 72 104 136 168 200 232 264	48 80 112 144 176 208 240	56 88 120 152 184 216 248	Variable ² (max 268)	SFU visit Variable ²	Un- scheduled visit (if applicable) ³	Early termination (if applicable) ¹	References (protocol section)
Visit type	Site	Site	Site	Site	Site	Site	Site	Tele- phone ⁴	Short Site	Tele- phone ⁴	Standard Site	Site	Site			
Visit window (days) ⁵	-3	NA	±3	±3	±3	±3	±3	±3	±3	±3	±3	±3	±3			
Patient-reported	d outcom	es (cont	inued)													
Worst Weekly Pruritus numeric rating scale Eczema-related																
Sleep numeric rating scale	X	X	X	X	X	X	X		X		X	X		X	X	11.3.2.4
Patient use of topical treatment ¹⁴																

- 1) If screening/baseline visits are performed on the same day as visit(s) in the parent trial, the order of assessments should be adhered to, working in parallel for both protocols. Assessments where data are captured in different vendor systems databases (ECG, ePRO, and laboratory tests) need to be completed twice. In such cases, the parent trial assessment should be performed first, followed by the trial LP0162-1337 assessment. For subjects included in the trial prior to protocol version 10, the first visit after May 2021 can be a site visit or a telephone visit.
- 2) Subjects who withdraw from the trial will be followed up as described in Section 10. The final safety follow-up visit will be 4 weeks after the last dose (i.e. 2 weeks after the EOT visit). For subjects from the parent trial LP0162-1334, the maximum number of weeks until the EOT visit will be 114 weeks.
- 3) Assessments and procedures to be performed at an unscheduled visit are at the discretion of the investigator. If the unscheduled visit involves administration of rescue treatment, the investigator should make every attempt to conduct efficacy and safety assessments (at least disease severity scores [IGA and EASI], concomitant medications/procedures, and AEs) immediately before administering any rescue treatment (see Section 9.5).

Trial ID: LP0162-1337

THIS DOCUMENT CONTAINS CONFIDENTIAL INFORMATION AND MUST NOT BE COPIED OR MADE AVAILABLE TO ANY THIRD PARTY WITHOUT THE PRIOR WRITTEN CONSENT OF THE LEO PHARMA GROUP

- 4) For subjects from the parent trial LP0162-1334, the telephone visit should preferably be performed as a video call.

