5.5 Ethical considerations

Participation in this long-term trial is voluntary and subjects can withdraw at any time. The subjects or their legally authorised representative(s) will give informed consent, and adolescent subjects will give informed assent (as appropriate and according to national laws and regulations). No vulnerable subject incapable of giving informed consent will be included in this clinical trial. Furthermore, female subjects who are pregnant, breastfeeding, or trying to become pregnant will not be included. Female subjects of childbearing potential who are sexually active, must agree to use a highly effective method of contraception to prevent pregnancy during the clinical trial and until 16 weeks after discontinuation of treatment with the investigational medicinal product (IMP). In addition, all female subjects of childbearing

Page 44 of 187

potential will have a pregnancy test performed before, during, and at end of treatment to ensure that no foetuses are exposed to the IMP.

In this trial, all subjects will be treated with open-label tralokinumab with optional use of TCS or TCI. All subjects have previously participated in one of the parent trials, and the subjects who have received tralokinumab in these trials are likely to have gained a certain degree of benefit since they have agreed to participate in a long-term extension trial. Subjects will be under supervision by a dermatologist or allergist at least every 8 weeks during the treatment period until end of May 2021. For subjects who re-consent/consent to participate in the trial after May 2021, supervision by a dermatologist or allergist occurs at least every 16 weeks after May 2021 and for the remaining treatment period to reflect standard clinical practice. Between site visits, a telephone visit is mandatory to secure sufficient safety reporting. Furthermore, subjects may receive rescue therapy at the discretion of the investigator if medically necessary through treatment and follow-up. Stopping rules are specified for this trial to ensure that subjects are not continuing in a trial where they experience no benefit or where their safety is not ensured.

Altogether, the risks associated with participating in this clinical trial are considered low and outweighed by the potential treatment benefit for each participating subject as well as the benefit of a potential future treatment option for moderate-to-severe AD.

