7.3 End of trial definition

The end of the trial is defined as the date of the last visit of the last subject in the trial globally. By the end of this trial, subjects will have been exposed to tralokinumab for up to 5 years, which is considered appropriate for evaluating long-term safety of tralokinumab.

The final collection of data for the primary endpoint will occur by Q2 2024.

A subject is considered to have completed the trial if the subject has completed all periods of the trial, including the safety follow-up visit, according to protocol version 13 or earlier versions.

The duration of the treatment period for each subject will depend on when the subject enters the trial after completing the parent trial, and by which treatment stop date they have consented to (end of May 2021, end of May 2022, or a country-specific end of treatment day according to Appendix 3J). Hence, a subject is considered to have completed the treatment period for either of the following scenarios:

- Approximately end of May 2021 for subjects completing according to earlier versions than protocol version 10.
- Approximately end of May 2022 for subjects from the parent trial LP0162-1334 who consented to continue in the trial after May 2021.
- At a country-specific end of treatment date (Appendix 3J) for subjects from the parent trials LP0162-1325, -1326, -1339, -1341, -1342, -1343, -1346, and TRA-WEI-0015-I who consented to continue in the trial after May 2021.

See Section 11.8 for the end of trial procedures.

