8.2 Inclusion criteria

For inclusion into this trial, subjects must fulfil all of the following criteria:

- Signed and dated informed consent has been obtained prior to any protocol-related procedures. Signed and dated informed consent for adolescent subjects must be provided by the subject's legal representative(s) and by the subject in the form of a signed and dated informed assent (as applicable according to national laws or regulations).
- 2. Subjects must have completed* the treatment period(s) of one of the parent trials: LP0162-1325, -1326, -1334, -1339, -1341, -1342, -1343, -1346, or TRA-WEI-0015-I.
 - *To be assessed on the first day of IMP administration (baseline).
- 3. Subjects must have complied with the clinical trial protocol in the parent trial to the satisfaction of the investigator.
- 4. Subjects must be able and willing to self-administer tralokinumab treatment (or have it administered by a caregiver) at home after the initial 3 injection visits at the trial site (in this trial).
- 5. Subjects must have applied a stable dose of emollient twice daily (or more, as needed) for at least 14 days prior to baseline.

6. Female subjects of childbearing potential (defined as Tanner stage ≥3 or menarche)* must use a highly effective** form of birth control (confirmed by the investigator) continuously for at least 1 month prior to the pregnancy test at baseline (Week 0), throughout the trial, and for at least 16 weeks (5 half-lives of the IMP) after the last administration of IMP.

- *A female subject is defined as not being of childbearing potential if she is:
 - Postmenopausal (at least 12 months with no menses without an alternative medical cause prior to screening), or surgically sterile (hysterectomy, bilateral salpingectomy, or bilateral oophorectomy).
 - Premenarchal.
- **A highly effective method of birth control is defined as one which results in a low failure rate (less than 1% per year) such as bilateral tubal occlusion, intrauterine device (IUD), intrauterine hormone-releasing system (IUS), combined (oestrogen- and progestogen-containing) hormonal contraception associated with inhibition of ovulation (oral, intravaginal, transdermal), progestogen-only hormonal contraception associated with inhibition of ovulation (oral, injectable, implantable), sexual abstinence (when this is in line with the preferred and usual life style of the subject), same-sex partner, or vasectomised partner (given that the subject is monogamous).

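### After May 2021, contraception runs to 16 weeks after the last dose but the last visit and pregnancy test are at 4 weeks, with no clear duty to report pregnancies in between

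*Protocol*

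**What the plan says.** Inclusion criterion 6 (Protocol Section 8.2) requires female subjects of childbearing potential to use highly effective contraception throughout the trial and "for at least 16 weeks (5 half-lives of the IMP) after the last administration of IMP". Section 5.5 repeats the requirement, for those who are sexually active: "to prevent pregnancy during the clinical trial and until 16 weeks after discontinuation of treatment".

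For subjects who re-consented or consented to treatment after May 2021, adolescents included, Section 4.2 (Panel 5, footnote 2) and Section 7.1.4 (Panel 8) put the only safety follow-up visit 4 weeks after the last dose. Panel 5 schedules the last urine pregnancy test at that visit. Subjects who stopped by end of May 2021 are followed to 16 weeks (Panels 4 and 8).

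Section 13.5 sets the reporting rule: "Any pregnancy occurring during the clinical trial must be reported to LEO Pharma within 24 hours of first knowledge". It gives no period after the last dose. Section 7.3 offers two possible end points. One is for the subject: "A subject is considered to have completed the trial if the subject has completed all periods of the trial, including the safety follow-up visit". The other is for the trial: "The end of the trial is defined as the date of the last visit of the last subject in the trial globally". For serious events, Section 13.4.1 states "SAEs occurring after the completion of the clinical trial, as defined in Section 7.3, should not be routinely sought or collected", and then asks for a report if the investigator learns of one. Section 13.5 has no matching sentence for pregnancies.

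**The concern.** The contraception requirement reflects how long drug is expected to remain in the body. The follow-up and testing schedule after May 2021 stops well before that point, and the reporting rule is not written to cover the remainder. If trial participation ends with the safety follow-up visit, a pregnancy conceived in weeks 4 to 16 need not be reported, and its outcome would not be followed, although residual drug is expected. Under the 16-week follow-up the same pregnancy fell within the subject's participation. The protocol itself lists interference with reproductive function among its theoretical potential risks (Section 5.6), so these are cases the sponsor would want to know about. The stake is patient safety; no planned analysis depends on it.

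**Working it through.** **Length of the gap.** Inputs: the end-of-treatment visit is 2 weeks after the last dose and the safety follow-up visit 2 weeks later (Section 4.2, Panel 5 footnote 2 and abbreviations); contraception lasts at least 16 weeks (Sections 5.5 and 8.2).

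- Final visit: 2 + 2 = 4 weeks after the last dose, which reproduces the protocol's figure.
- Gap: 16 − 4 = 12 weeks, or 12/16 = 75% of the contraception period. With the ±3-day visit window it is 11.6 to 12.4 weeks.
- Subjects who stopped by end of May 2021: 16 − 16 = 0 weeks.

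**Residual drug in the gap.** Assumptions: first-order elimination and no allowance for absorption after the last dose. The protocol equates 16 weeks with 5 half-lives, so the half-life is 16/5 = 3.2 weeks. A value of 3.0 weeks covers the possibility that 15 weeks was rounded up to 16. The fraction remaining at week t is 0.5^(t/half-life). The share of weeks 0–16 exposure falling after week 4 is (fraction at 4 − fraction at 16)/(1 − fraction at 16).

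| Half-life | Level at week 4 | Level at week 16 | Share of exposure after week 4 |
|---|---|---|---|
| 3.2 weeks | 0.5^(4/3.2) = 0.420 | 0.5^(16/3.2) = 0.031 | (0.420 − 0.031)/(1 − 0.031) = 0.40 |
| 3.0 weeks | 0.5^(4/3) = 0.397 | 0.5^(16/3) = 0.025 | (0.397 − 0.025)/(1 − 0.025) = 0.38 |

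**Does the reporting rule cover the gap?** This is a matter of reading the sections together.

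- Section 5.5 names the trial and the 16 weeks after discontinuation as separate periods. That favours ending the trial, for a subject, at her last visit.
- Section 13.2 collects adverse events until completion of the trial as defined in Section 7.3. In practice that works only at subject level.
- Section 13.7 separates a subject leaving the trial from the end of the trial. That favours the global reading.
- The requirement in Section 13.5 to follow pregnancies to their outcome governs follow-up. It does not set which pregnancies must be reported.
- The 4-weekly home tests in France (Appendix 4B) are recorded in the log of drug administration, and no testing period after treatment is stated.

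The text does not settle which reading applies.

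**The case against.** The strongest reply is that Section 13.5 speaks of the trial, and Section 7.3 gives only one definition of when the trial ends: the last visit of the last subject globally. On that reading most of the gap closes. Appendix 3J (approximate dates) has Poland ending treatment in May 2024 and every other country by May 2023, so the 16-week windows outside Poland would close by about September 2023, well before the global end. Only Polish subjects whose last dose falls in roughly the final 12 weeks would be uncovered: the trial would end 4 weeks after the very last dose, and 16 − 4 = 12. This is a fair reading, but the text does not compel it. Two sites could decide the same case differently, and on either reading nothing in the documents asks a subject to tell the site about a pregnancy after week 4.

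Several other points stand in part:

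- The shorter follow-up was deliberate and reasoned (Amendments 7 and 9), and testing at week 4 already goes beyond the testing scope in Section 5.5. The point here is the reporting window, not the visit schedule.
- Many adults may move to marketed tralokinumab, and residual trial drug is then not a distinct exposure.
- A congenital anomaly is an SAE (Appendix 1) and remains reportable if the investigator learns of it. A pregnancy without a serious event does not.
- A urine test at week 16 could also miss a very recent conception, so the 16-week schedule was not a perfect safeguard.
- The removed consent pages and the pregnancy forms, which are not in the documents, may instruct subjects or sites. That cannot be judged.
- The decay figures describe drug level, not missed reports or fetal risk.

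**Conclusion.** The concern holds. For subjects treated after May 2021, 12 of the 16 weeks of required contraception have no scheduled visit or pregnancy test, and Section 13.5 leaves it unclear whether a pregnancy in that interval must be reported. If completion is taken at subject level, the gap affects all of these subjects; on the global reading it shrinks to those who finish last. Roughly 40% of the drug level remains when scheduled follow-up stops (42% with a 3.2-week half-life, 40% with 3.0 weeks), assuming first-order elimination without late absorption. These figures do not apply to subjects who go on to marketed drug. The number of pregnancies affected cannot be derived from the documents. This is a low-cost patient-safety improvement; no estimate, analysis set or conclusion in the SAP is affected.

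**What to change.** Amend Section 13.5 so that any pregnancy with onset up to 16 weeks after the last dose of IMP is reported and followed to outcome, including when it comes to light after the safety follow-up visit. Have sites tell subjects at the final visit to notify them of such a pregnancy. If final visits have already taken place (the SAP describes the end of treatment in the past tense), a one-off request to sites for known pregnancies in that window would serve the same purpose. The cost is one sentence, one instruction and minor site effort after the last visit. No extra visit, test or SAP change is needed.
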